8.3.2. Outcome definitions

1.Regimen discontinuations: Discontinuation of CAB+RPV LA regimen for any reason during the study period will be captured, tabulated and reported.

Individuals who receive the oral lead-in but never initiate the CAB+RPV LA regimen will be tabulated separately but not included in the primary analysis.

Discontinuation of CAB +RPV LA will be defined as the latest date of the next scheduled injection which is missed and where bridging therapy has not been started. For example, for monthly dosing, if the first injection of CAB+RPV LA was received on June 1st, the second injection should be received on July 1st (allowed time window for second injection is June 24th to July 8th). The third injection should follow the timing of the first injection and should be received on August 1st (allowed time window for third injection is July 25th to August 8th). If not, date of discontinuation will be defined as August 8th (Monthly dosing).

For every 2 month dosing, if the first injection of CAB+RPV LA was received on June 1st, the second injection should be received on July 1st (allowed time window for second injection is June 24th to July 8th). The third injection should follow the timing of the first injection and should be received on September 1st (allowed time window for third injection is August 25th to September 8th). If not, date of discontinuation will be defined as September 8th (Every 2 month dosing).

Discontinuation will also be captured, tabulated and reported for any other CAB and/or RPV containing regimen.

Durability will be measured as proportion of individuals continuing on the regimen at the end of 6, 12 and 24 months.

Adherence will be assessed by estimating the number of individuals that missed one or more consecutive injections without taking daily oral bridging therapy or any other oral ARV regimen while not on CAB+RPV LA regimen and mean and median number of injections missed during a 12-month period. We will also estimate the number who received the injections seven or more days later than their scheduled injection visit and median duration of delayed injections in persons using bridging therapy.

In the standard follow-up data collection in EuroSIDA reasons for discontinuation are recorded as below.

Table 3. EuroSIDA – Reasons for Treatment Discontinuation

Code	Reason for Stopping Treatment
1	Treatment failure (i.e. virological, immunological, and/or clinical failure
1.1	Virological failure

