8.3.3. Confounders and effect modifiers

The study will examine the effect of potential confounders and effect modifiers as shown in Table 2 above on the risk for outcomes of interest.

Demographic variables

- Age
- Sex
- Route of HIV Infection
- Number of years since HIV diagnosis
- Ethnic origin
- Geographic region
- Date of ART initiation

Date CAB and/or RPV LA started

Virologic variables at regimen initiation

- HIV VL at initiation of CAB LA and/or RPV LA containing regimens (and in the 12 months prior to regimen start)
 - o Continuous (copies/mL)
 - o Categorical:
 - <50 copies/mL (or < LOD in clinics where LOD > 50 copies/mL)
 - $\ge 50 \text{ to } < 200 \text{ copies/mL}$
 - $\ge 200 \text{ to } < 10,000 \text{ copies/mL}$
 - \geq 10,000 to <100,000 copies/mL
 - \geq 100,000 copies/mL

Immunologic variables at regimen initiation

- CD4 cell count at initiation of CAB LA and/or RPV LA containing regimens (and in the 12 months prior to regimen start)
 - Continuous (cells/μL)
 - o Categorical:
 - CD4 \geq 500 cells/ μ L
 - CD4 count \geq 350 to <500 cells/ μ L
 - CD4 count <350 cells/µL
- CD4 nadir prior to initiation of CAB LA and/or RPV LA based ARV regimens

Clinical variables at regimen initiation

- HIV Subtype where available
- History of previous use of integrase inhibitor-based or NNRTI-based regimen
- History of previous antiretroviral exposure
- History of previous virologic failure
- History of previous HIV drug resistance and any historical HIV-1 subtype information, where available
- Body Mass Index (BMI), height, weight
- History of AIDS-defining Events (ADE)
- Concurrent medications (Etravirine, Rifampicin, Rifapentine, Rifabutin, Ribavirin, Ketoconazole, Fluconazole, Itraconazole, Clarithromycin, Erythromycin and other medications where data are available)
- Comorbidities (all defined to be consistent with published EuroSIDA analyses)
 - o HCV co-infection [3]
 - o HBV co-infection [4]
 - o End Stage Liver Disease (ESLD) (hepatocellular carcinoma, ascites, hepatorenal syndrome, grade III/IV hepatic

- encephalopathy, unspecified liver decompensation, oesophageal variceal bleeding, liver transplantation) [3]
- Cardiovascular Disease (CVD) (myocardial infarction, stroke, invasive coronary procedure) [3]

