Descriptive analyses will compare those with and without virologic failure to assess any differences in baseline characteristics of the two groups. Detailed analysis of additional risk factors will be limited to persons with 6, 12 or 24 months of follow-up. Multivariable logistic regression models will investigate the factors associated with virologic failure at 6 months, 12 months and 24 months after CAB+RPV LA initiation. Potential explanatory variables are listed above. We will also investigate the impact of missed doses and use of oral bridging therapy by using the data collected via the CRF. Multivariate analyses will be performed when > 30 persons on CAB+RPV LA have virologic failure and analyses will be limited to persons with > 6-, 12- or 24-months follow-up. The model building strategy will follow EuroSIDA protocol and include variables significant in univariate analyses as well as *a priori* pre-specified variables of interest. Primary analysis for clinical effectiveness will include individuals on CAB+RPV LA, with VL of <50/copies/mL at regimen initiation. In addition, all the analyses will be conducted separately for individuals on CAB+RPV LA with VL of ≥50 copies/mL at regimen initiation.

Our primary analyses of virologic outcomes will censor follow-up at discontinuation of CAB+RPV LA, last visit or death, whichever occurs first, an on-treatment approach to analysis. Sensitivity analyses will use an intent to treat approach and virologic outcomes will be assessed regardless of regimen discontinuation.

We will perform additional sensitivity analysis limited to those who start CAB+RPV LA with resistance data available, to confirm no present or past evidence of viral resistance to, and no prior virological failure with agents of the NNRTI and INSTI class.

AIM 4. Monitor for resistance and next treatment response among individuals who switched off CAB+RPV LA regimen

Monitoring for resistance

Since this is a non-interventional study aiming to capture individual care in real world setting, the study will not mandate resistance testing following discontinuation of the regimen of interest. Health care providers following the local treatment guidelines decide

what laboratory and resistance tests are to be conducted. Data thus generated will be captured and analyzed by the study team.

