case of resumption of LAI after missed second injection in two months or less, we will still consider it first exposure.

Similarly, the third injection (and injections thereafter) for the two-month schedule is given two months after the second injection and hence we will allow four months after the second injection to see if the regimen was resumed (≤3 months) or re-initiated (>3 months). In case of resumption of LAI after missed third injection in three months or less, we still consider it first exposure.

Treatment with long-acting antiretroviral therapy

Which long-acting antiretroviral drugs have been initiated? (drop down menu)

1) long acting cabotegravir + long acting rilpivirine

2) long acting cabotegravir without rilpivirine

3) long acting rilpivirine without cabotegravir

Dosage: 400/600 mg (CAB) / 600/900 mg (RPV) (drop down

menu)

Date of first injection: Year/month/day

Intended dosing schedule of long-acting antiretroviral therapy Monthly/Every 2 Month

HIV resistance testing (only pops up for the first injection and if CAB + RPV has been selected)

Has a HIV resistance test been performed prior to initiation of long-acting cabotegravir + rilpivirine yes/no

If yes

Date of latest most recent resistance test prior to initiation of long-acting antiretroviral therapy Year/month/day

Method used drop down menu

Please upload a copy of the resistance test report (result will be based on central review)

(After completion of date of first injection, a new section will open for second injection with target date one month after the first injection. All the questions below refer to subsequent injections after the first)

Has the patient received the next planned injection with long-acting antiretroviral drugs yes/no

If yes, Which long-acting antiretroviral drugs were given? (drop down menu)

1) long acting cabotegravir + long acting rilpivirine

2) long acting cabotegravir without rilpivirine

3) long acting rilpivirine without cabotegravir

Dosage: 400/600 mg (CAB) / 600/900 mg (RPV) (drop down

menu)

Date of injection: Year/month/day

Intended dosing schedule of long-acting antiretroviral therapy Monthly/Every 2 Month

(if the patient switches from monthly to two-monthly injections or vice versa, a new question pops up)

Reason for switching to monthly (or 2 monthly) injection schedule (drop down menu)

- 1. Convenience
- 2. To reduce cost
- 3. To reduce side effects
- 4. Personal reasons
- 5. Other (+ text field)

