(After completion of date of second injection, a new section will open for third injection with target date two month/3 months [for monthly and 2 monthly schedules, respectively] after the first injection. As long as the patient receives injections as scheduled, the target date for the next injection is determined by the start date ± 1 month/2 months ± 7 days for each injection depending on schedule)

(All injections until 24 months+ six weeks after initiation of LAI will be collected)

If no to question whether planned injection has been given, following question will appear:

	Has the patient started bridging therapy?								
		YES			NO				
If yes, new question will show:									
Reason for starting bridging therapy (LAI drugs out of stock,									
1 '	•	to come for the	•						
injection site	adverse effe	t, other + text fie	ld)						
Start date:				Has th	e patient	later res	started long-actin	g antiretroviral therapy?	
Stop date:									
			estion will show:						
Has the patie	nt restarted	ong-acting antire	troviral therapy?		YE	ES		NO	
	YES		NO						
Which long-ad		ive been given?	Reasons for	Which long-acti				Reasons for discontinuation	
long acting	2) long	3) long	discontinuation	long acting	2) long	•	3) long acting		
cabotegravir	acting	acting	(drop down	cabotegravir+	cabote	-	rilpivirine	*If death – please complete	
+ long	cabotegrav		menu with all	long acting	without		without	CoDe form	
acting	without	without	reasons in table	rilpivirine	rilpivirir	ne	cabotegravir	*If liver, other or unknown	
rilpivirine	rilpivirine	cabotegravir	3 in the					causes – please complete	
	• •	/ 600/900 mg	protocol)	Dosage: 400/60		B)/600/	900 mg (RPV)	hepatotoxicity form	
(RPV) (drop de	•			(drop down menu)			1		
Date of injecti			*If death —	Date of injection:			_		
	tended sche		please		ntended			1	
Monthly	Eve	y 2 Month	complete CoDe	Monthly		Every 2	Month		
			form						
			*If liver, other						
			or unknown						
			causes – please complete						
			hepatotoxicity						
			form						

(All those reported CAB + RPV discontinuations due to virological failure (reason 1, 1.1, 1.2) will prompt collection of resistance test results. A reminder will be sent after 1 and 2 years of follow up after failure. In addition to these specific reasons prompting collection of HIV resistance testing data, we will also perform checks for viral load>limit of detection to identify people with viral failure)

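### Dosing schedule (monthly or every 2 months) is recorded at each injection, but 8.3.3 does not name it as an explanatory variable and no Aim 2–4 result is set out by it

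*Protocol*

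**What the plan says.** **What is collected.** The case report form (Annex 1) asks for "Intended dosing schedule of long-acting antiretroviral therapy Monthly/Every 2 Month" at the first injection, at later injections and on restart, together with the dose. A change of schedule is captured with its reason: "if the patient switches from monthly to two-monthly injections or vice versa, a new question pops up". The recording span is long enough for the last Aim 3 time point: "All injections until 24 months+ six weeks after initiation of LAI will be collected".

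**What is defined.** Section 8.3.2 works through the two schedules separately. In the monthly example, a missed third injection gives 8 August as the discontinuation date. The other example begins "For every 2 month dosing, if the first injection of CAB+RPV LA was received on June 1st" and ends "If not, date of discontinuation will be defined as September 8th (Every 2 month dosing".

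**What is analysed.** Section 8.3.3 lists demographic, virologic and immunologic variables and "Clinical variables at regimen initiation". Neither schedule nor dose is among them, and neither is in Table 2. The Aim 2, 3 and 4 models in section 8.6 refer back to that list. Aim 3 adds missed doses and oral bridging ("Potential explanatory variables are listed above. We will also investigate the impact of missed doses and use of oral bridging therapy"), and Aim 4 adds missed and delayed doses and bridging. The named strata are viral load at initiation, drug combination (groups a–g) and, for Aim 5, region. The groups are defined by drugs, so both schedules fall in group a. The ENCePP checklist (Annex 2, item 5.4) answers No on whether exposure intensity is addressed, and its comment says that exposure is not categorised.

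**The concern.** Schedule is a main treatment characteristic that can differ between people within group a, and it enters several outcomes through their definitions. It sets how many injections can be missed or delayed in a year. From the second injection onward it also sets the discontinuation date. That date censors the primary on-treatment analysis of virologic outcomes and feeds the part of the virologic failure definition that combines one raised viral load with discontinuation within 4 months.

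If the schedule mix changes over five years, or differs between countries, a pooled figure can move although nothing has changed within either schedule. Region and LA start date are listed covariates, so they could pick up part of a schedule difference. Missed doses cannot stand in for schedule, because the number of planned doses itself differs. A drug utilisation study written for providers and regulators would then give outcomes without showing how they divide between the two schedules.

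**Working it through.** **1. Planned injections in the first 12 months (months 0 to 11), from 8.3.2 and Annex 1.**
- Monthly: months 0, 1, 2, …, 11, which is 12 injections.
- Every 2 months: months 0, 1, 3, 5, 7, 9, 11, which is 7 injections.

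After the first injection there are 11 and 6 chances to miss one. Assume, for illustration only, the same chance *p* of missing each. The chance of at least one miss is 1 − (1 − *p*)^k:

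| *p* (assumed) | Monthly, k = 11 | Every 2 months, k = 6 |
|---|---|---|
| 1% | 10.5% | 5.9% |
| 2% | 19.9% | 11.4% |

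Equal behaviour per injection gives unequal non-adherence per person, so the pooled per-person figure depends on the mix.

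**2. Discontinuation date, from the examples in 8.3.2.**
- Last injection 1 June (the first): the next window closes on 8 July on both schedules, which is 37 days. There is no difference.
- Last injection 1 July (the second): 8 August is 38 days later and 8 September is 69 days later, a difference of 31 days.

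**3. Pooled failure (illustration).** With assumed failure of 1% on one schedule and *q* on the other, and share *m* on the second, the pooled rate is 0.01(1 − *m*) + *q m*.
- *q* = 2%: 1.2% at *m* = 20% and 1.9% at *m* = 90%.
- *q* = 3%: 1.4% at *m* = 20% and 2.8% at *m* = 90%.

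The protocol gives no value for *q* or *m*.

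**4. What reporting by schedule costs in precision.** Table 4 gives 0.012 to 0.031 (width 0.019) for N = 1000, P = 0.02. Exact Clopper-Pearson limits for 20 of 1000 are 0.0123 to 0.0307 (width 0.0185), so the table row is reproduced. Splitting those 1000 people, with P = 0.02 in each part:

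| Assumed split | n | 95% limits | Width |
|---|---|---|---|
| 50:50 | 500 each | 0.0096–0.0365 | 0.027 |
| 80:20, larger part | 800 | 0.0115–0.0323 | 0.021 |
| 80:20, smaller part | 200 | 0.0055–0.0504 | 0.045 |

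**5. Power of a formal comparison** (N = 1000, split 50:50): 26% for 1% against 2%, 46% for 2% against 4%, and 62% for 1% against 3%.

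**6. Reach of the models.** Section 8.6 requires more than 30 events for the discontinuation and failure models, so at least 31. That needs 31/0.02 = 1550 people at 2% and 31/0.05 = 620 at 5%, but only 31/0.20 = 155 at 20%. At the low event rates in Table 4 a model term may never be fitted; at the higher rates it can be.

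**The case against.** The strongest reply is that this is analysis detail for the statistical analysis plan. The objectives ask about CAB+RPV LA as one regimen, the listed variables are called potential, section 8.6 itself adds form variables that are not in 8.3.3, and the models admit unnamed a priori variables. This stands in part: the list is not closed, and what can be shown is that schedule is not named. It does not dispose of the point. The protocol writes out a detailed list, names the dosing variables it wishes to add and leaves schedule out, and its checklist says that exposure is not categorised. Pooling is what the present text describes.

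Three stronger readings are tempting, and the protocol does not support them.
- *That region and calendar-time effects are confounded with schedule.* No schedule share by country or year is given, so this is only possible.
- *That readers will not learn the schedule mix at all.* Aim 2 promises frequency distributions of usage patterns, which could include it, though not outcomes by schedule.
- *That the dating rule biases the comparison throughout.* Each date follows that schedule's own next planned injection, and after the first injection the two dates coincide.

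It is also fair to say that the failure-rate illustration rests on an assumed two- to threefold difference. Even its widest movement (1.4% to 2.8%) lies inside the Table 4 interval for N = 1000, P = 0.02.

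**Conclusion.** The point holds as a gap in the analysis, not in data collection or in how outcomes are derived. Schedule is recorded and used for windows and discontinuation dates, but it is neither named as an explanatory variable nor used to set out any Aim 2–4 result. The firmest consequence is for adherence: a pooled count of missed injections per 12 months mixes 12 planned injections with 7. For durability, discontinuation and virologic failure, the pooled figure may partly reflect the schedule mix. How much cannot be derived from the protocol; the percentages in steps 1 and 3 of the working are illustrations under stated assumptions. Nothing here implies that either schedule performs better. Low power argues against a formal comparison of failure rates, but not against descriptive reporting.

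**What to change.** - **Section 8.3.3:** add intended dosing schedule at first injection as an a priori explanatory variable for the Aim 2, 3 and 4 models among people who started CAB+RPV LA. Leave it out of the model for not starting LA after the oral lead-in, because the form records schedule only once LA treatment has begun.
- **Schedule switches:** include an indicator for a switch before the assessment time. A time-updated term does not fit logistic models at fixed 6-, 12- and 24-month points.
- **Event rule:** use these terms only where the existing requirement of more than 30 events is met.
- **Tables:** beside each pooled figure, show by initial schedule the Aim 2 adherence (with planned injections as denominator), durability and discontinuation, the Aim 3 virologic outcomes and, where numbers allow, Aim 4 resistance. Label these as descriptive.

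**Cost.** No new data are needed: two entries in the variable list and extra table columns. Intervals within each schedule are wider (step 4 of the working), a formal comparison would have low power, and each fitted model carries one or two more terms.

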6.2. Rationale

There is a need to understand the CAB and/or RPV LA containing regimens utilization in a real-world clinical setting. Adherence to scheduled dosing visits to help maintain viral suppression and reduce the risk of viral rebound and potential development of resistance with missed doses is critical for long term maintenance of viral suppression. Impact of non-adherence on virologic failure and emergence of resistance need to be assessed in a real world clinical setting among a more heterogeneous population than often represented in clinical trials.

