2. Clinical effectiveness: Primary analysis for clinical effectiveness will include only those initiating the regimen per label i.e. initiating CAB+RPV LA with VL<50 copies/mL at regimen initiation. The following VL measures will be used for effectiveness assessment:

- 1. Proportion of individuals, virologically suppressed/undetectable (<50 copies/mL) at 6, 12 and 24 months following initiation of CAB+RPV LA regimen
- 2. Proportion of individuals with VL <200 copies/mL at 6, 12 and 24 months following initiation of CAB+RPV LA regimen
- 3. Proportion of individuals with confirmed virologic failure (CVF) during the first 6 months, and at 6, 12 and 24 months following initiation of CAB+RPV LA regimen defined as:
 - Two consecutive HIV RNA VL levels ≥200 copies/mL or
 - One HIV RNA VL level ≥200 copies/mL and regimen discontinuation within 4 months of VL ≥200 copies/mL

3. Resistance Testing:

Since this is a non-interventional study aiming to capture individual care in real world setting, the study will not mandate resistance testing following discontinuation of CAB+RPV LA regimen. Health care providers following the local treatment guidelines decide what laboratory and resistance tests are to be conducted. Data thus generated, including available HIV-1 subtypes, will be captured and analyzed by the study team.

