Descriptive statistics will describe and compare the ARV regimen individuals are switched to after discontinuation of CAB+RPV LA regimen. As resistance testing will not be common, we will describe the characteristics of those with and without resistance testing at virologic failure and again at virologic failure during the 12, 24, 36 and 48 months after switching regimens and use logistic regression to identify factors associated with resistance testing. Where more than 1 resistance test is available during the 12, 24, 36 and 48 months after stopping CAB+RPV LA regimen, cumulative resistance data will be collected and reported.

Study will monitor for resistance at virologic failure and again at virologic failure during the 12, 24, 36 and 48 months following the switch, where resistance data are available. Resistance patterns in those with resistance testing will be summarized. Depending on the number of resistance tests performed and amount of resistance detected, logistic regression will be used to identify factors associated with resistance to CAB+RPV LA. Potential explanatory variables are listed above including missed and delayed doses and use of bridging therapy.

Next treatment response

The study will describe virologic success at 12, 24, 36 and 48 months after discontinuation of CAB+RPV LA regimen, using virologic failure definition as described above. Given that this study involves persons in routine clinical care, and who may not attend clinic appointments every 12 months, a window of 12 weeks around the date in question will be used for virologic testing data. Thus, the proportion with virologic success at 12, 24, 36 and 48 months \pm 6 weeks will be used; and if none is available, the first measurement after 6 or 12 months will be used.

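### Missed doses and bridging are related to a failure outcome that itself partly contains a missed, unbridged injection, and no rule puts the dose before the raised viral load

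*Protocol*

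**What the plan says.** Four parts of the protocol meet here.

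- **Purpose.** Section 6.2: "Impact of non-adherence on virologic failure and emergence of resistance need to be assessed in a real world clinical setting".
- **Outcome.** Section 8.3.2 gives two routes to confirmed virologic failure. Route 1 is two consecutive viral loads of at least 200 copies/mL. Route 2 is "One HIV RNA VL level ≥200 copies/mL and regimen discontinuation within 4 months of VL ≥200 copies/mL".
- **Discontinuation.** Section 8.3.2 has it "defined as the latest date of the next scheduled injection which is missed and where bridging therapy has not been started".
- **Analysis.** Section 8.6, Aim 3, examines factors for failure at 6, 12 and 24 months and adds: "We will also investigate the impact of missed doses and use of oral bridging therapy by using the data collected via the CRF". Aim 4 takes the same dosing variables into the resistance models: "Potential explanatory variables are listed above including missed and delayed doses and use of bridging therapy".

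Two definitions of a missed dose are available. Objective 2a and section 8.3.2 count people who "missed one or more consecutive injections without taking daily oral bridging therapy or any other oral ARV regimen while not on CAB+RPV LA regimen". The combined definition, objective 2c, exempts only those who took bridging. Aim 3 does not say which one it uses.

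**The concern.** A route 2 failure cannot exist without a discontinuation, and a discontinuation is a missed, unbridged injection. The same event can then enter the model on both sides: as the exposure, and as the component that turns a single raised viral load into a failure. Bridging prevents a missed injection from being a discontinuation, so it also prevents that miss from completing a route 2 failure. Bridging can therefore look protective for the same reason.

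The order in time is open as well. Annex 1 collects all injections up to 24 months plus six weeks. It records a decision to stop, or a switch of regimen, under the same branch as any other planned injection that was not given. An injection withheld because the viral load had risen can therefore be read as a missed dose that explains the failure.

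At stake is the question that section 6.2 names. An inflated estimate for missed doses, or a flattering one for bridging, would go to the regulators and healthcare providers listed in section 11.2.

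**Working it through.** The protocol gives no figure for this association, so there is none to reproduce. The check is first logical, then illustrative.

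**1. Does the overlap survive the primary analysis?** Aim 3 censors follow-up at discontinuation, restricts the models to people with more than 6, 12 or 24 months of follow-up, and uses windows of ±6 weeks. Take a person with a viral load of at least 200 at month 12 whose injections stop at month 14. The value lies in the 12-month window, follow-up exceeds 12 months, and the stop comes 2 months later, inside the 4-month limit. The person can count as a 12-month failure, and the only missed dose follows the raised value. The censoring event is the same missed injection that completes the failure. The intent-to-treat sensitivity analysis ignores discontinuation for follow-up but keeps the failure definition, so the overlap remains there too.

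**2. How large could the definitional part be?** Suppose a missed, unbridged injection has no effect on viral load. All inputs are assumptions, as the protocol gives none of them:

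- q = probability of at least one value of at least 200 (0.02 to 0.10)
- c = probability that the next value is also at least 200 (0.2 to 0.9)
- d = probability of discontinuation within 4 months in a person not counted as having missed (0.05 to 0.20)
- t = probability that the missed injection falls within 4 months of the raised value (0.33 to 1)

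P(failure | missed) = q[c + (1−c)(t + (1−t)d)]

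P(failure | not missed) = q[c + (1−c)d]

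| Case | q | c | d | t | Missed | Not missed | Odds ratio |
|---|---|---|---|---|---|---|---|
| Lowest in grid | 0.02 | 0.9 | 0.20 | 0.33 | 0.0189 | 0.0184 | 1.03 |
| Moderate | 0.05 | 0.5 | 0.20 | 0.33 | 0.0366 | 0.0300 | 1.23 |
| Moderate | 0.05 | 0.5 | 0.05 | 1 | 0.0500 | 0.0263 | 1.95 |
| Highest in grid | 0.10 | 0.2 | 0.05 | 1 | 0.1000 | 0.0240 | 4.52 |

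For the third row: 0.05 × (0.5 + 0.5 × 1) = 0.0500; 0.05 × (0.5 + 0.5 × 0.05) = 0.02625; odds ratio = (0.0500/0.9500)/(0.02625/0.97375) = 1.95.

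The ratio exceeds 1 whenever c < 1, d < 1 and t > 0. Read the other way, bridged misses compared with unbridged misses would show the reciprocal in the two moderate rows: 1/1.23 = 0.81 and 1/1.95 = 0.51.

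**3. Does removing the overlap remove the effect?** With failure limited to route 1, both groups have risk q × c, and the odds ratio is 1.00. This assumes that a second viral load is equally available in both groups.

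**4. A related inconsistency.** Section 8.3.2 dates discontinuation at the end of the injection window. Annex 1 treats resumption within 2 months (second injection) or 3 months (third and later injections) as continued first exposure. The two must be reconciled, because they decide which missed doses are discontinuations.

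**The case against.** The strongest reply has five parts.

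- **The oral ARV exemption.** Under objective 2a a person stopped for failure and switched to another oral regimen is not counted as having missed. Section 6.1 calls an alternative suppressive regimen essential after stopping, so many planned switchers would leave the exposed group. This stands as a limit on size. It is not a defence, because objective 2c lacks the exemption and Aim 3 names neither definition.
- **Order.** A reader might infer that every route 2 failure has its missed dose after the raised value. The text does not support that: it sets a 4-month distance and no order. Some misses may come first, which is the path the study wants to see.
- **Windows and follow-up limits.** A viral load raised at month 8 with injections stopped at month 10 may look like the typical case. It is not a failure in the 6- or 12-month primary model. Month 8 lies after the 6-month window closes (about month 7.4) and before the 12-month window opens (about month 10.6), and follow-up on treatment ends before month 12. The month 12 and 14 case shows that the limits narrow the problem without closing it.
- **Purpose.** The ENCePP checklist says no specific hypotheses are tested, and the multivariable model runs only with more than 30 failures. Both are true, but section 6.2 still asks for the impact of non-adherence.
- **Detail for the SAP.** Time windows for covariates often belong there, and none is shown. But the outcome, the definition of discontinuation and the planned analysis are all fixed in this protocol, and they overlap as written.

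**Conclusion.** The point holds as a partial overlap of definitions combined with a missing rule on order. The direction follows from the definitions: upward for missed doses, apparently protective for bridging. The size does not. The range of about 1.03 to 4.5 rests on four assumed inputs and on misses that are independent of viral load.

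A reader might infer that the models will report a large effect even when there is none. If 30% to 70% of failures carried a miss that only reflected stopping, and 5% to 20% of non-failures had a miss, the null odds ratio would be roughly 3 to 48. Nothing in the protocol supports those shares, so the supportable statement is that the estimate is inflated by an unknown amount, and by more if many stops are caused by failure.

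Nor does the definitional argument reach everything. Route 1 failures need no discontinuation, and the resistance outcome in Aim 4 does not contain one. Doses withheld after a raised value there are ordinary reverse causation.

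**What to change.** - In the Aim 3 failure models, count only missed, delayed or bridged doses dated between the first injection and the first viral load of at least 200. For non-failures, count up to the viral load used for that 6-, 12- or 24-month assessment.
- Do not count an injection missed on or after the first value of at least 200. Keep misses that precede it, even if they later define discontinuation. A blanket exclusion of the miss that defines discontinuation would, under section 8.3.2, also delete genuine unbridged misses that came before rebound.
- State whether the objective 2a or 2c definition of a missed dose applies.
- Apply the same ordering to the dosing variables in the Aim 4 resistance models.
- As a check, repeat the missed-dose analysis with failure limited to two consecutive values of at least 200.

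The cost is a short change of wording and a date restriction in programming. Planned and actual injection dates are already on the CRF (section 8.3.1 and Annex 1). The estimated effect of missed doses will be smaller.
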